### 16.3. OTHER EFFICACY ANALYSES

Paired correlation (Pearson or Spearman, as appropriate) and p-value between each of the following endpoints will be provided by treatment group based on the mITT:

- Change from Baseline in ESS total score to the end of period
- Change from Baseline in type 1 and 2 of average sleep latency time on MWT to the end of period
- Change from Baseline in MDS-UPDRS Part III total score to the end of period
- Change from Baseline in Apathy total score to the end of period
- Change from Baseline in FSS total score to the end of period
- Change from Baseline in SCOPA-Cog total score to the end of period
- PGlc
- CGlc

For each of these endpoints, descriptive statistics will also be provided by treatment group for each PGlc category (see Section 16.2.1.4) based on the mITT. A histogram plot of the mean change from Baseline to end of period visit in ESS total score by CGlc/PGlc category at the end of period visit will be provided by treatment group based on the mITT.

A scatter plot of the change from baseline to the end of treatment period in ESS total score versus the change from baseline to the end of treatment period in type 1 and 2 of average sleep latency time on MWT will be provided by treatment group based on the mITT.

[figure not shown]
Number and percentage of subjects with an ESS total score  $\leq 10$  and  $>10$  will be provided by visit and treatment group based on the mITT, but no statistical inference will be performed.

[figure not shown]
### 17. SAFETY OUTCOMES

All outputs for safety outcomes will be based on the SAF and, unless otherwise specified, presented by treatment group (JZP-110 75 mg, JZP-110 150 mg, JZP-110 300 mg, and placebo), regardless of the sequence and period. Summaries will also be presented for the pooled JZP-110 treatment groups, when applicable (i.e., incidences and shifts from Baseline), as well as by sequence for Placebo, but regardless of the period.

For subjects who received Sequence C, the following rules will be followed to compute the descriptive statistics, incidences and shifts from Baseline:

- For descriptive statistics, the average of the non-missing values collected at the end of each treatment period will be used;
- For incidences, each subject will be counted only once for each category;
- For shifts from Baseline, the worst value among the non-missing values collected at the end of each treatment period will be used.

For the summaries on the pooled JZP-110 group, the same rules than for the subjects who received Sequence C will be followed for the incidences and shifts from Baseline.

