### **3.4. SAMPLE SIZE JUSTIFICATION**

[figure not shown]
Approximately 49 subjects will be randomized to the 3 sequence groups (A, B, and C) with the goal of 40 subjects completing the study: 34 subjects in Sequences A and B, and up to 6 subjects in sequence C. The randomization ratio implemented will be 3:3:1 with expected randomization of subjects to sequences being approximately 21:21:7.

Although the primary objective of this study is to assess safety, efficacy endpoint-based power calculations were performed for reference. A sample size of 34 subjects (assuming 17 completing in each of the Sequences A and B) will provide 80% power to detect a difference of 3 points in the change from Baseline in ESS score between 1 of the JZP-110 and placebo groups not adjusting for multiple comparisons. This calculation assumes a common standard deviation (SD) of 6 points for the change from Baseline in ESS score and a 2-sided significance level of 0.05 using an analysis of variance (ANOVA)-based t-test for difference of means in a crossover design. The primary purpose of placebo Sequence C is to preserve study blinding.

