## 14. STUDY DRUG EXPOSURE

Exposure to study drug, in days, will be summarized overall and by sequence across all periods and by period based on the SAF. Exposure will also be summarized by treatment group (including all JZP-110 doses pooled into one group) and broken down further by sequence for the placebo treatment group based on the mITT. Interruptions, treatment compliance, and dose changes will not be taken into account for duration of exposure.

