## 17.1. ADVERSE EVENTS

Adverse events will be coded to SOC and PT using the MedDRA dictionary (version 18.0) and will be classified as follows:

- **Prior AEs** are defined as AEs that started on or after the signature of the informed consent but prior to the first dose of study drug (i.e., first dose in Period 1) and have not worsened in severity on or after the first dose of study drug;
- **Treatment-emergent adverse events (TEAEs)** are defined as any AEs that started or worsened in severity on or after the first dose of study drug;

Only TEAEs will be summarized; listings will include all AEs (see APPENDIX 1 for handling of partial dates for AEs). AEs will be reported under the treatment group being received when AE first occurs/worsens. Should an AE with a partially missing onset date can be assigned to more than one treatment group, it will be reported under the active treatment group with the lowest dose. For TEAEs that started during the safety follow-up period, TEAEs will be attributed to the last treatment group received in the study.

An overall summary of number and percentage of subjects within each of the categories described in the following subsections (e.g., all TEAEs, SAEs, AEs leading to discontinuation of study drug, etc.) will be provided. A similar overall summary will be presented for the subset of TEAEs that started during the safety follow-up period.

For TEAEs summarized by SOC and PT, SOC will be sorted in alphabetical order and the PTs within each SOC will be sorted in descending frequency order for the pooled JZP-110 treatment group. For PT only tables, incidence will be sorted similarly to the PTs in the summaries by SOC and PT.

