### 17.1.1. ALL TEAEs

Incidence of TEAEs will be presented by SOC and PT. If a subject reports a TEAE more than once within a SOC or PT, the TEAE will be reported only once for that SOC or PT. Incidence of TEAEs will be similarly presented by PT only.

Incidence of TEAEs by SOC and PT will also be presented by maximum severity and relationship to study drug.

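### SAP 17 and 17.1 set once-per-subject TEAE percentages side by side in columns that cover unequal time: for completers 1.0 week at 75 and 150 mg, 1.5 at 300 mg, 2.0 on placebo, 3.5 pooled

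*SAP*

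**What the plan says.** Section 17 of the SAP presents safety outputs for 75 mg, 150 mg, 300 mg and placebo without regard to sequence or period, adds a pooled JZP-110 column for incidences and shifts, and also shows results "as well as by sequence for Placebo, but regardless of the period". For Sequence C, "For incidences, each subject will be counted only once for each category"; for shifts, "the worst value among the non-missing values collected at the end of each treatment period will be used". The pooled group follows the same two rules.

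Section 17.1 reports the number and percentage of subjects and assigns each event to the treatment at onset. It adds: "For TEAEs that started during the safety follow-up period, TEAEs will be attributed to the last treatment group received in the study". It also plans this: "A similar overall summary will be presented for the subset of TEAEs that started during the safety follow-up period". Under Section 17.1.1, for repeat events within a SOC or preferred term, "the TEAE will be reported only once for that SOC or PT".

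Section 14 plans exposure separately: "Exposure to study drug, in days, will be summarized overall and by sequence across all periods and by period based on the SAF". Exposure by treatment group is planned on the mITT, not the safety population. The SAP text links neither summary to an adverse event table.

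**The concern.** Counting each subject once is sound when the columns cover about the same time. Here they do not, for three reasons:

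- Sequence C contributes four placebo weeks per subject.
- The pooled column spans three active weeks.
- For completers, the follow-up week is added to 300 mg in Sequence A and to placebo in Sequences B and C.

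Safety and tolerability is the primary objective and is answered descriptively, so reading across these columns is the primary result. Placebo is raised against 75 and 150 mg, which can hide a modest excess. The 300 mg column is raised against the lower doses by follow-up alone, which can look like a dose step. Pooled JZP-110 is raised against placebo, which can look like a drug effect. Preferred terms are also sorted by the pooled column, the one with the longest time.

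**Working it through.** **Inputs.** Allocation 3:3:1 of 49 (SAP 3.4). Four 7-day periods, the sequence table and a follow-up visit about 7 days after the last dose (SAP 3.1). Routine AE recording up to the final visit (Protocol 6.14.1.5). Attribution of follow-up events (SAP 17.1).

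**The plan's own figure.** 49 × 3/7 = 21 and 49 × 1/7 = 7, so 21:21:7 reproduces.

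**Mean weeks per column** = sum of (n × weeks) / contributing subjects (49 for placebo, 42 otherwise).

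| Column | On treatment | With one week of follow-up |
|---|---|---|
| 75 mg, 150 mg | 1.0 | 1.0 |
| 300 mg | 1.0 | (21×2 + 21×1)/42 = 1.5 |
| Placebo | (21×1 + 21×1 + 7×4)/49 = 70/49 = 1.43 | (21×1 + 21×2 + 7×5)/49 = 98/49 = 2.0 |
| Pooled | 3.0 | (21×4 + 21×3)/42 = 3.5 |

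On-treatment person-weeks are 70 on placebo (A 21, B 21, C 28), 42 at each dose and 126 pooled.

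**Sensitivity to completion.** The SAP plans "with the goal of 40 subjects completing the study: 34 subjects in Sequences A and B, and up to 6 subjects in sequence C". With 17:17:6, placebo is 58/40 = 1.45 on treatment and 81/40 = 2.025 with follow-up; the other columns do not change. If instead 4, 4 and 1 subjects leave A, B and C after Period 1, 2 or 3 (timing assumed), the means with follow-up are 1.0–1.1 weeks at 75/150 mg, 1.5–1.55 at 300 mg, 1.96–2.02 on placebo and 3.3–3.5 pooled.

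**Effect on percentages.** Assume the same constant weekly risk r on every treatment, so the chance of an event over w weeks is 1 − (1 − r)^w. At r = 10%, w = 1, 2, 3, 4, 5 gives 10.0, 19.0, 27.1, 34.4, 41.0%.

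- With follow-up: 75/150 mg 10.0%; 300 mg (21×19.0 + 21×10.0)/42 = 14.5%; placebo (21×10.0 + 21×19.0 + 7×41.0)/49 = 18.3%; pooled (21×34.4 + 21×27.1)/42 = 30.7%.
- On treatment: each dose 10.0%; placebo (42×10.0 + 7×34.4)/49 = 13.5%; pooled 27.1%.
- Pooled/placebo at weekly risks of 2, 5, 10 and 20%: 1.74, 1.72, 1.68, 1.60 with follow-up; 2.08, 2.06, 2.01, 1.91 on treatment.

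**Early clustering.** Let weeks after the first on placebo, or after the first active week for pooled, carry f × 10%. On treatment, placebo = [42(0.10) + 7(1 − 0.9(1 − 0.1f)³)]/49 and pooled = 1 − 0.9(1 − 0.1f)². For f = 0.5, 0.25, 0, placebo is 11.8, 10.9, 10.0%, pooled is 18.8, 14.4, 10.0%, and the ratio is 1.59, 1.32, 1.00.

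**Do person-week rates solve it?** Not under clustering. At f = 0 with no drug effect, a dose has 4.2/42 = 0.10 subjects with an event per person-week and placebo 4.9/70 = 0.07, a ratio of 1.43. At f = 0.5 and 0.25 it is 1.21 and 1.31.

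**Does A+B placebo solve it?** It equalises time, not period. If risk falls with study week (assumed 10% in week 1, 5% in weeks 2–4) and the drug is inert, A+B placebo is (10 + 5)/2 = 7.5%, 75 mg is (5 + 10)/2 = 7.5%, and 150 and 300 mg are 5.0%.

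**The case against.** The plan is not blind to this. Placebo is split by sequence, and for completers Sequence A placebo is one week with no follow-up, so a planned column already matches 75 and 150 mg in time. Sequence C is displayed on its own. Follow-up events have an overall summary, and exposure by sequence and period allows on-treatment person-time to be rebuilt. All of that stands. It does not correct the all-placebo, 300 mg or pooled columns, and the follow-up summary is not stated to be by SOC or preferred term.

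SAP Section 8 leaves table format to shells that are not part of the public text. Headers or footnotes there may already show person-time; only its absence from the SAP text can be asserted.

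The percentages rest on assumed risks. That is also true, and it limits what can be said about size, though not the week counts.

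A reader might go further in four ways that the documents do not support:

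- **Bias in one direction.** The distortion is mixed: against the drug in one comparison, in its favour in another.
- **A 30-day tail.** Appendix 1 counts TEAEs to 30 days after the last dose, which suggests much longer columns. But the last-treatment rule covers only events starting in the safety follow-up period, and Table 4 ends that window at last dose + 8, or at the early termination visit if later. No attribution rule is stated beyond it, and routine recording stops at the final visit.
- **A+B placebo as a clean comparator.** It remains tied to period, as shown above.
- **Descriptive tables wholly unaffected.** Each Sequence C subject enters as an average of up to four values, which can narrow the placebo SD.

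**Conclusion.** The concern holds as a matter of presentation. The once-per-subject columns cover 1.0, 1.0, 1.5, 2.0 and 3.5 weeks on average for completers, and these figures follow directly from the design. With no drug effect and a constant 10% weekly risk they would read 10.0, 10.0, 14.5, 18.3 and 30.7%. That size is illustrative: it needs equal, constant risk, full completion at 21:21:7 and one week of follow-up, and it falls to nothing if later weeks carry no risk. Confidence is high in the week counts and not in the size of any distortion.

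Visit-based ECG and vital-sign incidence and shift tables share the problem to a lesser degree, because Sequence C is any or worst of four visits and pooled is any or worst of three. The data are sound and nothing in the trial's conduct needs to change. This is an inexpensive correction worth making because these tables carry the primary objective.

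**What to change.** In SAP 17 and 17.1, and in the table shells:

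1. Base the main SOC/preferred-term treatment columns on on-treatment onset. Show follow-up-onset TEAEs separately by SOC and preferred term, labelled by last treatment. Table 4 already starts follow-up the day after the last dose, which can serve as the cut.
2. Label pooled JZP-110 as any of three weeks, do not compare it directly with placebo, and print on-treatment person-weeks in every column header (planned: placebo 70, each dose 42, pooled 126).
3. Show one-week, on-treatment placebo from Sequences A and B as a time-matched reference, with A, B, C and all-placebo beside it. State that it equalises time but not period: A's placebo is all in Period 1, and B's is all in Period 4, straight after 300 mg without washout. If risk falls with study week, an inert 150 or 300 mg could look protective.
4. Footnote visit-based incidence and shift tables with the four-visit and three-visit rules, and note that Sequence C averaging can narrow the placebo SD in descriptive tables.

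Person-week rates, if added, should be supportive only.

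The cost is slightly wider tables and more programming, with no new data. The A+B reference uses 42 of the 49 placebo subjects. At 10%, the 95% half-width 1.96 × √(0.1 × 0.9/n) goes from 8.4 to 9.1 points, and the other seven subjects remain displayed.

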#### 16.1.5. SENSITIVITY ANALYSIS OF KEY EFFICACY ENDPOINT

- **Sensitivity to carry-over effect from the end of period 3 to end of period 4 in Sequence B** (i.e., from JZP-110 300 mg to placebo): ESS total score observed values at end of treatment period for Period 3 and end of treatment for Period 4 for subjects randomized into Sequence B as well as the change from Baseline to each end of the treatment period will be summarized using descriptive statistics by treatment group based on the mITT.

The key efficacy analysis will be repeated adjusting the model for carry-over effect of Period 3 on Period 4, by adding an effect-type coding variable for the 4 treatment groups representing the residual treatment effect of the treatment taken during the previous period as fixed effects (Kuehl, 2000):

Treatment Group	Residual effect of JZP-110 300 mg, x
JZP-110 75 mg	0
JZP-110 150mg	0
JZP-110 300 mg	1
Placebo	-1

In other words, if a subject is randomized to Sequence A (i.e., placebo, JZP-110 75 mg, JZP-110 150 mg, and JZP-110 300 mg), the variable x will be set to the following on Period 4 subject record to represent the treatment group with which the subject was treated during the previous period (i.e., JZP-110 150 mg): x = 0. If a subject is randomized to Sequence B (i.e., JZP-110 75 mg, JZP-110 150 mg, JZP-110 300 mg, and placebo), the variable x will be set to the following on Period 4 subject record to represent the treatment group with which the subject was treated during the previous period (i.e., JZP-110 300 mg): x = 1. Finally, if a subject is randomized to Sequence C (i.e., placebo, placebo, placebo, and placebo), the variable x will be set to the following on Period 4 subject record to represent the treatment group with which the subject was treated during the previous period (i.e., placebo): x = -1.

Log Likelihood and degrees of freedom for each model (adjusted and not adjusted for carry-over effect) will be presented. To assess the significance of the carry-over effect, a likelihood ratio test will be performed as follows: the difference of the ‘-2 residual likelihood fit statistic’ (-2logL) between the 2 models (i.e., -2logL of model no adjusted - -2log L of adjusted model) will be tested using a Chi-square test at 0.05 alpha level with a degree of freedom defined as the difference between degrees of freedom of model adjusting for carryover effect minus degrees of freedom of model not adjusting for carryover effect.

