### 17.3. ECG EVALUATIONS

The following ECG parameters will be reported for this study based on core laboratory values:

- HR (beats per minute [bpm])
- RR interval (msec)
- PR interval (msec)
- QRS interval (msec)
- QT interval (msec)
- QT Fridericia's correction (QTcF) interval (msec) [derived]
- QT Bazett's correction (QTcB) interval (msec) [derived]
- Overall evaluation of ECG:
  - Normal
  - Abnormal, not clinically significant
  - Abnormal, clinically significant

The following summaries will be provided based on SAF for ECG data:

- Observed values and change from Baseline to end of period post-dose timepoint (for quantitative measurements)
- Observed values and change from end of period pre-dose timepoint to end of period post-dose timepoint (for quantitative measurements)
- Incidence of markedly abnormal criteria from Baseline to end of period post-dose timepoint (refer to Section 17.3.2 for details) by gender
- Incidence of markedly abnormal criteria from end of period pre-dose timepoint to end of period post-dose timepoint (refer to Section 17.3.2 for details) by gender
- Shift from Baseline to end of period post-dose timepoint in ECG overall evaluation by gender
- Shift from end of period pre-dose timepoint to end of period post-dose timepoint in ECG overall evaluation by gender

- Incidence of subjects for which their ECG overall evaluation improved, remained unchanged or worsened from Baseline to end of period post-dose timepoint by gender
- Incidence of subjects for which their ECG overall evaluation improved, remained unchanged or worsened from the end of period pre-dose timepoint to the end of period post-dose timepoint by gender
- Incidence of subjects with at least one ECG diagnosis by diagnosis category (i.e., rate/rhythm, conduction abnormalities, changes in ST segment, axis, chamber enlargement, myocardial infarction, and miscellaneous) and diagnosis by visit, timepoint, and gender

The following listings will be provided:

- Listing of subjects with any observed QT, QTcB, or QTcF values >450 msec and/or change from Baseline in QT, QTcB, or QTcF >30 msec
- Listing of subjects with any abnormal ECG overall evaluation

The following figures will be provided:

- Line plot of mean observed values across visit by sequence and treatment group;

[figure not shown]

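### ECG and vital-sign shift and incidence tables score pooled JZP-110 on up to three visits, Sequence C placebo on up to four and every other column on one, so pooled JZP-110 has no like-for-like placebo column

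*SAP*

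**What the plan says.** SAP section 17 has safety outputs "presented by treatment group (JZP-110 75 mg, JZP-110 150 mg, JZP-110 300 mg, and placebo), regardless of the sequence and period". It adds a pooled JZP-110 column for incidences and shifts, and shows placebo "as well as by sequence for Placebo, but regardless of the period".

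Subjects in Sequence C have four placebo periods, so the section sets rules for combining them. For shift tables: "For shifts from Baseline, the worst value among the non-missing values collected at the end of each treatment period will be used". For incidence tables: "For incidences, each subject will be counted only once for each category". It then extends both: "For the summaries on the pooled JZP-110 group, the same rules than for the subjects who received Sequence C will be followed" for incidences and shifts.

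The tables concerned are:

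- the shifts in respiratory rate (17.4.1) and in seated blood pressure and pulse (17.4.2), using the Low and High limits in Table 6;
- the blood pressure and pulse change thresholds (17.4.2);
- the ECG shifts and markedly abnormal criteria (17.3);
- a three-way ECG table: "Incidence of subjects for which their ECG overall evaluation improved, remained unchanged or worsened from Baseline to end of period post-dose timepoint by gender".

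Laboratory abnormalities are not affected, because SAP 3.6 reduces them to a listing. Protocol 9.2 rules out inference on safety endpoints.

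**The concern.** Safety is the primary objective and no safety test is planned, so these descriptive columns are the evidence and will be read side by side. Under the rules above they do not estimate the same quantity. The more visits a subject contributes, the more chances there are to cross a limit by ordinary variation. A pooled JZP-110 subject has up to three chances, a Sequence C placebo subject up to four, and a Sequence A or B subject one in the placebo column. Nothing in section 17 adjusts for this. A reader comparing pooled JZP-110 with placebo would see an excess that the scoring rule alone can produce.

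Two further gaps need no assumed rate. On a scale with both a Low and a High end, the rule does not say which value is worst when a subject is Low at one visit and High at another; one of the two findings is lost. Under the count-once rule, a subject whose ECG improves at one visit and worsens at another falls in both categories, so the percentages in that table can exceed 100%.

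**Working it through.** The documents state no expected abnormality or shift rate, so there is no plan figure to reproduce. The check asks what the columns would show with no drug effect.

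**Inputs from the documents**
- Visits per subject (SAP Table 1): Sequences A and B have 1 placebo and 3 active periods; Sequence C has 4 placebo and 0 active.
- Planned allocation (SAP 3.4): 21:21:7, so 42 subjects with one placebo visit and 7 with four. Only the 42 enter the pooled column.

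**Assumptions**
- Single-visit rate p: 5%, 10% or 20%.
- Between-visit correlation ρ on a latent normal scale: 0 to 0.9.
- All visits are non-missing.

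**Formulas**
- P(k) is the probability of at least one abnormal result in k visits. With ρ = 0, P(k) = 1 − (1 − p)^k. With ρ > 0, P(k) is 1 minus the average of (1 − q(x))^k over a standard normal x, where q(x) = Φ((√ρ·x − z)/√(1 − ρ)) and z is the upper-p normal quantile.
- Pooled JZP-110 = P(3). Each dose column and Sequence A or B placebo = p. Sequence C placebo = P(4).
- Overall placebo = (42p + 7·P(4))/49.

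**Worked case, p = 10%, ρ = 0**
- P(3) = 1 − 0.9³ = 27.1%; P(4) = 1 − 0.9⁴ = 34.4%.
- Overall placebo = (42 × 0.10 + 7 × 0.344)/49 = 13.5%.
- Pooled to overall placebo = 27.1/13.5 = 2.01.

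| p | ρ | Pooled P(3) | Sequence C P(4) | Overall placebo | Pooled ÷ overall placebo | Pooled ÷ A or B placebo | One dose ÷ overall placebo |
|---|---|---|---|---|---|---|---|
| 5% | 0 | 14.3% | 18.5% | 6.9% | 2.06 | 2.85 | 0.72 |
| 5% | 0.5 | 11.8% | 14.4% | 6.3% | 1.87 | 2.37 | 0.79 |
| 5% | 0.9 | 8.0% | 8.8% | 5.5% | 1.44 | 1.59 | 0.90 |
| 10% | 0 | 27.1% | 34.4% | 13.5% | 2.01 | 2.71 | 0.74 |
| 10% | 0.5 | 21.8% | 25.9% | 12.3% | 1.78 | 2.18 | 0.82 |
| 10% | 0.9 | 15.0% | 16.3% | 10.9% | 1.37 | 1.50 | 0.92 |
| 20% | 0 | 48.8% | 59.0% | 25.6% | 1.91 | 2.44 | 0.78 |
| 20% | 0.5 | 38.9% | 44.4% | 23.5% | 1.65 | 1.94 | 0.85 |
| 20% | 0.9 | 27.8% | 29.8% | 21.4% | 1.30 | 1.39 | 0.93 |

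Using the completer targets (34 in A and B, 6 in C) moves the pooled-to-overall ratio by no more than 0.03.

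**Does the by-sequence placebo split help?** Each dose column has a like-for-like comparator in Sequence A and B placebo, one visit each, with an expected ratio of 1. Pooled JZP-110 has none. Against A or B placebo the no-effect ratio is 1.39 to 2.85. Against Sequence C it is P(3)/P(4), from 14.3/18.5 = 0.77 to 27.8/29.8 = 0.93, and that column holds about 7 subjects.

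**Counting by subject-visit instead.** At full attendance pooled JZP-110 has 42 × 3 = 126 visits and placebo has 42 + 7 × 4 = 70. Each visit is abnormal with probability p, so the expected ratio is 1.00 for any ρ.

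**The case against.** The case for leaving the rule alone has real content.

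- **Placebo is also shown by sequence.** This answers any worry about the individual doses. A reader might infer that every dose looks safer than it is because overall placebo is inflated. The documents do not support that, since each dose can be set against Sequence A and B placebo. The inflation itself is small in subjects: at p = 5% it is 7 × (P(4) − p), about 0.3 to 0.9 of one subject in 49.
- **The multiple depends on assumptions.** A reader might infer that pooled JZP-110 will look about twice as abnormal as placebo. That needs correlation near zero. Section 17.4.2 averages several readings per visit, which removes noise. Change criteria subtract the same Baseline from every visit, which alone gives a correlation of about 0.5 if error variances are equal and the subject's mean is stable. At 0.5 the ratio is 1.65 to 1.87.
- **Worst is clear for the overall ECG evaluation**, which is an ordered three-level scale. The gap concerns only Low/Normal/High tables.
- **Means use the Sequence C average while shifts use the worst value.** A reader might call this a contradiction. It is not: the two displays answer different questions, and pooled summaries are limited to incidences and shifts.
- **An ever-abnormal count is a conventional, cautious safety display**, and here the pooled bias runs against the drug. The fault lies in placing it beside single-visit rates without a label.
- **The table shells cited in SAP section 8 are not available here**, so footnotes or denominators that might help cannot be checked.

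What remains is that the split gives pooled JZP-110 no matching placebo column. The protocol's by-sequence vital-sign and ECG summaries (9.13.2, 9.13.4) might have allowed one, but SAP 3.6 drops them except within placebo. The SAP does equalise visits elsewhere: for CGIc and PGIc, section 16 takes only the period 1 assessment from Sequence C.

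**Conclusion.** The point holds for ECG and vital-sign shift and incidence tables. Pooled JZP-110, which contains only Sequence A and B subjects, is an up-to-three-visit figure. Overall placebo mixes one-visit and up-to-four-visit figures. With no drug effect the pooled-to-overall-placebo ratio is about 1.3 to 2.1, for an assumed single-visit rate of 5-20% and latent correlation of 0-0.9. Subjects who stop early contribute fewer visits, which would shrink it somewhat.

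The direction follows from the rule and the sequence layout whenever findings vary between visits; the size is conditional on figures the documents do not give. The undefined worst value for two-sided scales and the overlapping improved/unchanged/worsened counts follow from the text alone. No test or decision rule uses these tables, so the harm is a misleading description of the primary objective, not an invalid inference. It should be corrected.

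**What to change.** In SAP section 17:

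- For scheduled ECG and vital-sign measurements, tabulate shifts and threshold incidences in the overall placebo and pooled JZP-110 columns by subject-visit, with the number of visits as denominator. Each visit then falls in exactly one shift or improved/unchanged/worsened category.
- Keep any ever/worst subject count as a separate line, labelled with the number of visits per subject. On that line compare pooled JZP-110 only with Sequence C over three matching periods (2 to 4 for Sequence A, 1 to 3 for Sequence B).
- Count Low and High separately, so that a subject with both appears under each.

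The cost is a few lines of SAP text and some programming, with no new data. Denominators become visits, whereas protocol 9.13.2 and 9.13.4 ask for the number and percentage of subjects; the separate ever line retains that. Sequence C would supply 28 of 70 placebo visits (40%) from 7 subjects, so the visit counts should be printed. The ever comparison with Sequence C will be imprecise at that size.
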